6.4.2.2 Objective Response

The objective response (OR) is defined as PR or CR, which is determined by the investigator according to RECIST v1.1. Patients without post-baseline information will be counted as non-responders.

The same analyses for CBR will be conducted on the objective response rate.

6.4.2.3 Duration of Objective Response

Duration of response (DOR) is defined as time from the first occurrence of a documented objective response to the time of the first documented disease progression (as determined by the investigator according to RECIST v1.1) or death from any cause, whichever occurs first. Data for patients without the occurrence of disease progression or death as of the clinical data cut-off date will be censored at the time of the last tumor assessment.

DOR will be estimated using the Kaplan-Meier methodology, with patients grouped according to the treatment arm assigned at randomization. Only patients achieving a CR or PR will be included in the assessment of DOR.

6.4.2.4 Overall Survival

OS is defined as the time from randomization to death from any cause. Data for patients who are alive at the time of the analysis data cut-off will be censored at the last date they were known to be alive. Data from patients without postbaseline information will be censored at the date of randomization plus 1 day.

The same analyses for PFS will be conducted for OS.

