Protocol WO40181 has been amended to address recent data available from the primary analysis. At the primary analysis of this study (clinical cut-off date of 5 August 2020), a higher proportion of deaths was observed in the venetoclax plus fulvestrant arm compared with the fulvestrant arm. Additionally, the venetoclax plus fulvestrant arm did not demonstrate a numerical improvement in the primary endpoint of clinical benefit rate (CBR) or the secondary endpoint of progression-free survival (PFS) compared with the fulvestrant arm. Changes to the protocol, along with a rationale for each change, are summarized below:

- The study rationale and benefit-risk assessment has been updated to indicate that, based on the results of the primary analysis, it is no longer considered appropriate for patients in this study to receive venetoclax. As of 8 October 2020, all active patients in the venetoclax plus fulvestrant arm of the study will be requested to discontinue the venetoclax treatment immediately, and will be given the option to continue fulvestrant treatment alone (Section 1.4).
- Language regarding the study design, study treatment, and treatment interruption has been updated to reflect the immediate discontinuation of venetoclax treatment (Sections 3.1, 4.3.2.1, 5.1.3.2, Appendix 1).
- The frequency of survival follow-up has been increased from approximately every 6 months to approximately every 3 months or more frequently after treatment discontinuation, to enhance safety data collection (Sections 3.1, 4.6.1, Appendix 1). Furthermore, language has been added to clarify that new anti-cancer therapy after study drug discontinuation should be reported once known (Appendix 1).

Additional changes made to the protocol are as follows:

- On the basis of the updated fulvestrant Summary of Product Characteristics, language pertaining to the use of contraception has been updated to indicate that contraception should be used for up to 2 years after the last dose of study drug, or based on local prescribing information for fulvestrant (Sections 4.1.1, 5.1.1.5).
- Adverse events of special interest for the study have been modified to remove hepatitis B reactivation (Section 5.2.3)
- The Medical Monitor has been changed and emergency medical contact information updated accordingly (Section 5.4.1).
- The reference safety information document for venetoclax has been updated to Venetoclax Investigator's Brochure for solid tumour studies (Section 5.7).

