4.6 TREATMENT, PATIENT, STUDY, AND SITE DISCONTINUATION

4.6.1 Study Treatment Discontinuation

Patients must permanently discontinue study treatment if they experience any of the following:

- Any medical condition that the investigator or Sponsor determines may jeopardize the patient's safety if he or she continues to receive study treatment

- Investigator or Sponsor determines it is in the best interest of the patient (including high-grade toxicities when continuing treatment is deemed detrimental)
- Pregnancy
- Use of an anti-cancer therapy not required per protocol
- Disease progression

The primary reason for study treatment discontinuation should be documented on the appropriate eCRF. Patients who discontinue study treatment prematurely will not be replaced.

Patients will return to the clinic for a treatment completion or treatment discontinuation visit 28 days (+3 days) after the last dose of study drug (see [Appendix 1](#) for additional details).

After treatment discontinuation due to disease progression, information on survival follow-up and new anti-cancer therapy will be collected via telephone calls, patient medical records, and/or clinic visits approximately every *3 months, or more frequently*, until death, loss to follow-up, withdrawal of consent, or study termination by the Sponsor, whichever occurs first.

Patients who are discontinued from study treatment for reasons other than disease progression and have started follow-on treatment/s will be followed for survival approximately every *3 months, or more frequently*, until death, lost to follow-up, withdrawal of consent, or study termination by the Sponsor, whichever occurs first.

Patients who are discontinued from study treatment/s for reasons other than disease progression and have not started follow-on treatment/s will be followed for disease status every 8 weeks (± 5 days) from the date of randomization until Week 24 (± 5) days and every 12 weeks (± 5 days), thereafter, until disease progression, loss to follow-up, withdrawal of consent, death or study termination by the Sponsor, whichever occurs first (see [Appendix 1](#) for additional details).

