5.3.5.8 Deaths

For this protocol, mortality is an efficacy endpoint. Deaths that occur during the protocol-specified adverse event reporting period (see Section 5.3.1) that are attributed by the investigator solely to progression of MBC should be recorded on the Death Attributed to Progressive Disease eCRF. All other deaths that occur during the adverse event reporting period, regardless of relationship to study drug, must be recorded on the Adverse Event eCRF and immediately reported to the Sponsor (see Section 5.4.2).

Death should be considered an outcome and not a distinct event. The event or condition that caused or contributed to the fatal outcome should be recorded as the single medical concept on the Adverse Event eCRF. Generally, only one such event should be reported. If the cause of death is unknown and cannot be ascertained at the time of reporting, "**unexplained death**" should be recorded on the Adverse Event eCRF. If the cause of death later becomes available (e.g., after autopsy), "unexplained death" should be replaced by the established cause of death. The term "**sudden death**" should not be used unless combined with the presumed cause of death (e.g., "sudden cardiac death").

Deaths that occur after the adverse event reporting period should be reported as described in Section 5.6.

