Appendix 1 Schedule of Activities (cont.)

- ^a Patients who do not initially meet all eligibility criteria may be re-screened once within 2 weeks, given that the reason for screening failure was not ER or HER-2 status (see Section 4.5.1).
- ^b Patients will continue subsequent cycles every 28 days (\pm 3 days of scheduled treatment day) until disease progression, death, loss to follow up, withdrawal of consent, or study termination by the Sponsor (Section 3.3), whichever occurs first.
- ^c All patients who discontinue study treatment will return for a study drug discontinuation visit 28 days after last dose (up to 3 days of delay [to Day 31] is acceptable)
- ^d For patients who discontinue study treatment early for reasons other than disease progression and have not started follow-on treatment. These patients will be followed every 8 weeks (\pm 5 days) from the date of randomization until Week 24 (\pm 5 days) and every 12 weeks (\pm 5 days), thereafter, until disease progression death, loss to follow-up, withdrawal of consent, or study termination by the Sponsor, whichever occurs first.
- ^e Follow-up of survival and anti-cancer treatment will be conducted *approximately every 3 months, or more frequently*, from disease progression for all patients until death, loss to follow-up, withdrawal of consent, or study termination by the Sponsor, whichever occurs first. The same survival follow-up will be done for patients who discontinue study treatment early for reasons other than disease progression and have started follow-on treatment.
- ^f Cycle 1 Day 2 (i.e., 24-hour) visit is required only for the first 10 patients enrolled in each arm. A chemistry panel to monitor for TLS (see Section 5.1.1.1) will be collected and must include at least electrolytes, uric acid, phosphorous, calcium, and creatinine levels.
- ^g Complete physical examination includes an evaluation of the head, eyes, ears, nose, and throat, and the cardiovascular, dermatologic, musculoskeletal, respiratory, gastrointestinal, genitourinary, and neurologic systems.
- ^h Vital signs to include body temperature, respiratory rate, pulse rate, and systolic and diastolic blood pressure while the patient is in a seated position. Height and BSA are only required at screening. Subsequent BSA is required if there is a $>10\%$ change in weight.
- ⁱ A bone scan is to be performed within 28 days prior to Cycle 1 Day 1. See Section 4.5.5.1 for further instructions.

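### Survivors off treatment are censored at their last contact, with no vital-status check at the cut-off, so each arm's OS curve can be biased downward if late deaths are learned sooner than alive-dates.

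*Combined protocol and SAP*

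**What the plan says.** - **Censoring.** Under Section 6.4.2.4, data for patients alive at the cut-off "will be censored at the last date they were known to be alive".
- **Contact off treatment.** Under Section 4.6.1, after progression, "information on survival follow-up and new anti-cancer therapy will be collected via telephone calls, patient medical records, and/or clinic visits". Appendix 1 footnote e sets the interval at "approximately every 3 months, or more frequently", running "from disease progression for all patients until death, loss to follow-up, withdrawal of consent, or study termination by the Sponsor". Patients who stopped early and began another therapy follow the same schedule.
- **Off treatment without progression or new therapy.** "These patients will be followed every 8 weeks" until Week 24, and every 12 weeks after that (footnote d).
- **Late deaths.** "Deaths that occur after the adverse event reporting period should be reported as described in Section 5.6" (Section 5.3.5.8). Section 5.6 acts when the investigator becomes aware of a serious event believed related to study drug. Section 4.6.2 allows public records to be used for patients who withdraw.
- **Cut-off.** The primary analysis falls no later than 6 months after the last patient enters (Section 6.4). No section links a survival contact or status check to any cut-off.

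**The concern.** The contact clock starts at a different date for each patient, so a cut-off date falls at a random point between two contacts. A living patient leaves the risk set at the last contact. A patient who dies after that contact counts as an event if the site hears of the death before the database is read. When that happens, deaths are complete to the cut-off but survivors' time is not, and the Kaplan-Meier curve sits too low.

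The off-treatment period is where the events occur. By Section 1.4, 26 of the 28 deaths (17 and 9) came more than 28 days after the last dose. At stake are the absolute OS figures in each arm: the curve, the median and the landmark rates.

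**Working it through.** **1. The documents' own OS figures (Section 1.4).** There were 19 + 9 = 28 deaths among 103 patients, and 28/103 = 27.2%, as stated. The arm percentages match 19/51 = 37.3% and 9/52 = 17.3% (arm sizes inferred). The interval 1.11 to 5.89 is consistent with the hazard ratio of 2.56: √(1.11 × 5.89) = 2.56. No sample size or power is stated for OS.

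**2. Assumptions, none of them from the documents.**
- Exponential survival, calibrated so that the expected deaths equal 19/51 and 9/52.
- Follow-up to cut-off uniform over 3–18 or 6–24 months.
- Median time to stopping treatment 2 or 4 months.
- Contact every 28 days on treatment and every 3 months afterwards.
- *q* = the share of deaths after the last contact that are learned before the analysis.

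**3. The gap.** Off treatment it is spread over roughly 0 to 3 months, so it averages close to 1.5 months. Counting survivors still on treatment, the average is 1.2 to 1.5 months.

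**4. Hazard inflation when *q* = 1.** All deaths count, and only survivors' time is lost. With *D* the share dead, λ the true hazard and *g* the mean gap among survivors:

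mean person-time PT = *D*/λ; inflation = PT / [PT − (1 − *D*) × *g*]

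| Follow-up, arm | *D* | λ per month | PT (months) | *g* (months) | Inflation |
|---|---|---|---|---|---|
| 6–24, venetoclax | 0.3725 | 0.0320 | 11.64 | 1.36 | 11.64/(11.64 − 0.85) = 1.08 |
| 6–24, control | 0.1731 | 0.0128 | 13.5 | 1.47 | 13.5/(13.5 − 1.22) = 1.10 |
| 3–18, venetoclax | 0.3725 | 0.0463 | 8.05 | 1.39 | 8.05/(8.05 − 0.87) = 1.12 |
| 3–18, control | 0.1731 | 0.0184 | 9.41 | 1.41 | 9.41/(9.41 − 1.17) = 1.14 |

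The first row uses a median of 4 months on treatment and the others 2 months. A large-sample simulation gives the same range, 8% to 14%. Adding the discontinuation visit 28 days after the last dose leaves the size much the same.

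**5. Other values of *q*.** At *q* = 0.5 the inflation is about half. At *q* = 0 it is nil.

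**6. On the OS scale (*q* = 1).** Twelve-month OS is too low by 1.3 to 4.0 points with venetoclax (for example 53.4% against a true 57.4%) and by 0.6 to 2.3 points in control (for example 77.9% against 80.2%).

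**7. Hazard ratio (*q* = 1).** It is 2.46 to 2.49 against a true 2.50 to 2.52. Both arms are inflated by similar factors, so the ratio shifts only slightly, towards 1.

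**8. Earlier contact interval.** The summary of changes says: "The frequency of survival follow-up has been increased from approximately every 6 months to approximately every 3 months or more frequently". With 6-month contacts and *q* = 1 the hazard inflation would be 17% to 32%, and the hazard ratio 2.43 to 2.45. This bears on how to read absolute OS at the 5 August 2020 cut-off. It is not a fault in the current text.

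**9. With the check in place.** If vital status is confirmed at the cut-off for every patient, inflation is 1.00 in both arms. With 90% confirmed and *q* = 1, about 1% remains at 3-month contacts.

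**The case against.** Censoring at the last date known alive is a conventional rule, and the bias needs an asymmetry that the documents do not establish. The route through Section 5.6 covers events believed related to study drug, whereas 24 of the 28 deaths (16 and 8) were from progressive disease more than 28 days after the last dose. Public records are mentioned only for patients who withdraw. No section says that sites hear of such deaths between contacts. Medical records can update alive-dates as well as deaths, and Appendix 1 footnote aa asks for new anti-cancer therapy to be reported as soon as it is known, which also refreshes an alive-date. The calculation gives survivors no such updates.

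All of this stands, and it makes the finding conditional. A reader might infer that OS *is* understated in each arm. The documents support only that it can be, because *q* is unknown and could be zero.

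The absence of a check from the protocol also does not show that none was planned or done operationally. What survives is that the text does not require one, so the size of *q* is left to chance.

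**Conclusion.** The point holds as a conditional one, and it is minor. OS is a secondary endpoint. The current text leaves survivors censored on average 1.2 to 1.5 months before the cut-off. If late deaths are learned ahead of alive-dates, each arm's hazard can be inflated by up to about 8% to 14%, under the assumed follow-up, time on treatment and exponential survival calibrated to the observed deaths.

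Three stronger readings are not supported:

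- **That this explains the hazard ratio of 2.56.** The ratio hardly moves, and the small shift is towards 1.
- **That the decision to stop venetoclax is in doubt.** Section 1.4 rests it on the results overall: no numerical improvement in clinical benefit rate or PFS, and 19 against 9 deaths. Death counts do not depend on how survivors are censored.
- **That survival contact was made more frequent to strengthen the OS analysis.** The stated reason in the summary of changes is better safety data.

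The primary clinical benefit analysis does not use the OS censoring rule and is unaffected.

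**What to change.** - **Section 4.6.1 and Appendix 1 footnote e:** for each remaining OS analysis, require a vital-status check by call or record review, on or shortly after the clinical cut-off (a fixed window such as 2 weeks would do). It should cover every patient in both arms who is not known dead and has not withdrawn from survival contact.
- **Section 6.4.2.4:** state that patients confirmed alive on or after the cut-off are censored at the cut-off date. This also settles the case of an alive-date later than the cut-off. Deaths after the cut-off need no new rule, because those patients already count as alive at the cut-off.

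The cost is one round of calls or record checks per OS cut-off, which "approximately every 3 months, or more frequently" already allows. No visit or procedure is added. Patients who cannot be reached, or who withdrew without any record, keep the gap, so the report should give the number confirmed in each arm.

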6.5 SAFETY ANALYSES

The safety analyses will include all randomized patients who received at least one dose of venetoclax or fulvestrant (the safety population) with patients grouped according to the treatment actually received.

Drug exposure will be summarized to include duration of treatment, number of doses, and intensity of dose.

All adverse events occurring during or after the first study drug dose will be summarized by treatment arm and NCI CTCAE grade. In addition, serious adverse events, adverse events of special interest, and adverse events leading to study drug discontinuation or interruption will be summarized accordingly. Multiple occurrences of the same event will be counted once at the maximum severity.

Deaths reported during the study treatment period and those reported during the safety follow-up period will be summarized by treatment arm.

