2. OBJECTIVES AND ENDPOINTS

This study will evaluate the efficacy of venetoclax (GDC-0199; ABT199) in combination with fulvestrant compared with fulvestrant alone in women with ER+, HER2-negative, locally advanced breast cancer not amenable to surgical or local therapy with curative intent or with MBC who experienced disease recurrence or progression during or after being treated with CDK4/6i therapy for at least 8 weeks prior to progression. Specific objectives and corresponding endpoints for the study are outlined in [Table 1](#).

Table 1 Objectives and Corresponding Endpoints

Objectives	Corresponding Endpoints
Primary Efficacy Objective:	

 To evaluate the efficacy of venetoclax in combination with fulvestrant compared with fulvestrant alone 	
 Clinical benefit defined as CR, PR, or SD lasting ≥ 24 weeks from randomization in patients with measurable disease at baseline, as determined by the investigator according to RECIST v1.1.
Secondary Efficacy Objective:	

 To evaluate the efficacy of venetoclax in combination with fulvestrant compared with fulvestrant alone 	
 PFS, defined as the time from randomization to the first occurrence of disease progression (as determined by the investigator according to RECIST v1.1) or death from any cause, whichever occurs first Objective response, defined as CR or PR, as determined by the investigator according to RECIST v1.1 DOR, defined as time from the first occurrence of a documented objective response to the time of the first documented disease progression (as determined by the investigator according to RECIST v1.1) or death from any cause, whichever occurs first OS, defined as the time from randomization to death from any cause
Safety Objective:	

 To evaluate safety and tolerability of venetoclax in combination with fulvestrant compared with fulvestrant alone 	
 To evaluate safety and tolerability of venetoclax in combination with fulvestrant compared with fulvestrant alone
Pharmacokinetic Objectives:	

 To assess the pharmacokinetics of venetoclax and fulvestrant following administration of venetoclax in combination with fulvestrant 	
 Plasma concentrations of venetoclax and fulvestrant at specified timepoints

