- **Control arm:** fulvestrant 500 mg administered as two 250-mg IM injections on Cycle 1 Days 1 and 15, and then on Day 1 of each subsequent 28-day cycle. No crossover to the venetoclax arm is permitted.

Tumor assessments will be conducted for all patients at screening and at every 8 weeks (± 5 days) from the date of randomization until Week 24 (± 5 days) and every 12 weeks (± 5 days) thereafter. Tumor assessments will be conducted regardless of dose delays or early discontinuation, until investigator-assessed disease progression (as specified below), the predefined end of the study (Section 3.3), or until death, whichever occurs first.

Study treatment for each patient will continue until disease progression, unacceptable toxicity, withdrawal of consent, death, or study termination by the Sponsor, whichever occurs first.

Diagnosis of disease progression should be supported by radiology assessments as per RECIST v1.1. All patients who are discontinued from all study treatment will return for a study drug discontinuation visit 28 days (+3 days) after the last dose of study treatment.

Patients who are discontinued from study treatment for reasons other than disease progression and have started follow-on treatment will be followed for survival approximately every *3 months, or more frequently*, until death, loss to follow-up, withdrawal of consent, or study termination by the Sponsor, whichever occurs first.

Patients who are discontinued from study treatment for reasons other than disease progression and have not started follow-on treatment will be followed for disease status every 8 weeks (± 5 days) from the date of randomization until Week 24 (± 5 days) and then every 12 weeks (± 5 days) thereafter until disease progression, death, loss to follow-up, withdrawal of consent, or study termination by the Sponsor, whichever occurs first.

[figure not shown]
After disease progression, patients will be followed for survival and subsequent anti-cancer therapies approximately every *3 months, or more frequently*, until death, loss to follow-up, withdrawal of consent, or study termination by the Sponsor, whichever occurs first.

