5.3.1 Adverse Event Reporting Period

Investigators will seek information on adverse events at each patient contact. All adverse events, whether reported by the patient or noted by study personnel, will be recorded in the patient's medical record and on the Adverse Event eCRF.

After informed consent has been obtained but prior to initiation of study drug, only serious adverse events caused by a protocol-mandated intervention (e.g., invasive procedures such as biopsies, discontinuation of medications) should be reported (see Section 5.4.2 for instructions for reporting serious adverse events).

After initiation of study drug, all adverse events will be reported through 28 days after the last dose of study drug (venetoclax or fulvestrant, whichever is later). After this period, investigators should report any deaths, serious adverse events, or other adverse events of concern that are believed to be related to prior study drug treatment as prescribed in Section 5.6.

Instructions for reporting adverse events that occur after the adverse event reporting period are provided in Section 5.6.

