6.1 DETERMINATION OF SAMPLE SIZE

Approximately 100 patients need to be recruited and randomized in a 1:1 ratio to two treatment arms (venetoclax + fulvestrant and fulvestrant). The study will enroll both BCL-2 high ($\geq 50\%$ of tumor cells stained with an intensity of IHC 2⁺ or 3⁺) and low

($\geq 50\%$ of tumor cells stained with an intensity of IHC 0 or 1+ and $< 50\%$ IHC 2+ or 3+) patients, and it is planned to enroll approximately 50 BCL-2-high patients.

The sample size of 100 patients provides precision of 15% for 80% CI when calculating the absolute difference in the CBR between the two arms assuming the expected observed CBR in the control arm is 40% (Cristofanilli et al. 2016) and in the venetoclax arm is 60% (i.e., the 80% CI for difference in CBR is from 5% to 35%).

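### Adverse events are summarized as once-per-patient counts by arm with no measure of observation time, so crude proportions can mislead for persistent-hazard events if time on treatment differs between arms

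*Combined protocol and SAP*

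**What the plan says.** The safety objective in Section 2 is comparative: "To evaluate safety and tolerability of venetoclax in combination with fulvestrant compared with fulvestrant alone".

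Section 6.5 sets the analysis. "All adverse events occurring during or after the first study drug dose will be summarized by treatment arm and NCI CTCAE grade". Serious AEs, AEs of special interest and AEs leading to discontinuation or interruption are handled in the same way, and "Multiple occurrences of the same event will be counted once at the maximum severity". The section also states: "Drug exposure will be summarized to include duration of treatment, number of doses, and intensity of dose". Nothing links that exposure table to AE incidence. No rate per patient-time, time to first event, cumulative incidence or common-window comparison is named.

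Two other sections fix how long each patient is observed. Section 5.3.1 says that "all adverse events will be reported through 28 days after the last dose of study drug", counted from the later of venetoclax or fulvestrant. After that, Sections 5.3.1 and 5.6 ask only for events believed related to study drug. Section 3.1 says: "Study treatment for each patient will continue until disease progression, unacceptable toxicity, withdrawal of consent, death, or study termination by the Sponsor".

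**The concern.** Each patient's window for full AE collection is time on treatment plus 28 days. Time on treatment is determined after randomization, mostly by progression, and so may differ between arms. A once-per-patient proportion divides by patients, not by time. The arm observed for longer will therefore show more patients with an event even if the weekly risk is identical.

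At stake is how the by-arm AE tables answer a comparative objective. If the combination delays progression, it gathers extra AEs from longer observation. If its patients stop sooner, a real excess of harm looks smaller than it is. The plan handles unequal follow-up for progression-free survival, duration of response and overall survival with time-to-event methods, but has nothing equivalent for AEs.

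**Working it through.** The documents give no figure for this effect, so there is nothing of the plan's to reproduce. The calculation below shows how large it could be.

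**Inputs from the documents**
- Planned clinical benefit rate (CBR): 60% versus 40% (Section 6.1), judged at 24 weeks (Section 6.4.1).
- Enrolment about 18 months (Section 3.3); primary analysis no later than 6 months after last patient in (Section 6.4). Follow-up F at cut-off then runs from 6 to 24 months, or 26.1 to 104.4 weeks.
- A 28-day (4-week) tail after the last dose in both arms (Section 5.3.1).

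**Assumptions not in the documents**
- The CBR stands in for the proportion still on treatment at 24 weeks.
- Time on treatment T is exponential, and entry is uniform.
- The AE hazard μ is constant and the same in both arms.

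**Step 1: stopping hazards.** λ = −ln(S)/24, where S is the proportion still on treatment at 24 weeks.
- Venetoclax: −ln(0.60)/24 = 0.0213 per week, mean 47.0 weeks.
- Control: −ln(0.40)/24 = 0.0382 per week, mean 26.2 weeks.
- Hazard ratio: 0.0213/0.0382 = 0.56.

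**Step 2: mean AE window.** The window is min(T + 4, F). For a given F its mean is 4 + [1 − exp(−λ(F − 4))]/λ. Averaged over F, this gives 36.6 versus 26.6 weeks, a ratio of 1.38.

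**Step 3: proportion with at least one event.** For a given F this is the integral from 0 to F of μ·exp(−μt)·R(t). R(t) is 1 up to week 4 and exp(−λ(t − 4)) after it. The result is averaged over F. The true rate ratio is 1.00 throughout.

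| Control proportion | Venetoclax proportion | Crude ratio |
|---|---|---|
| rare-event limit | – | 1.38 |
| 10% | 13.5% | 1.35 |
| 30% | 38.4% | 1.28 |
| 50% | 60.4% | 1.21 |
| 70% | 79.0% | 1.13 |
| 90% | 93.9% | 1.04 |

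**Step 4: how far the result depends on the assumptions**
- Follow-up limited to 24 weeks: the crude ratio is only 1.04 to 1.13.
- Equal time on treatment: 1.00.
- Shorter treatment with venetoclax (illustrative 35% versus 40% at 24 weeks): the window ratio is 0.92, and at a weekly hazard of 1% the crude ratio is 0.93.
- A true rate ratio of 1.5 with a control hazard of 1% per week: the crude ratio is 1.38 at equal durations. It falls to 1.26 and 1.12 if the venetoclax arm stops treatment with an assumed hazard ratio of 1.2 and 1.5.
- AE hazard confined to the first 4 weeks: 1.00. Confined to the first 8 weeks: 1.01 to 1.02.

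**Step 5: would a rate per patient-time repair it?** Under a constant hazard, yes: it returns 1.00. With the hazard confined to the first 4 to 8 weeks and no true difference, the first-event rate ratio is 0.73 to 0.76. The longer-observed arm then looks about 25% safer, because event-free later time swells its denominator.

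**Step 6: is Weeks 0-8 a fair common window?** With the 4-week tail, the proportion still observed at week 8 is exp(−4λ). That is 92% versus 86%, even in a model that lets progression be declared before the first scheduled scan at week 8.

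**The case against.** - **Section 6.5 is descriptive.** It plans no test, ratio or interval for AEs, and Section 6.9 calls the study hypothesis-generating. Treatment duration is tabulated in the same section, so a difference would be visible. This stands, and it limits the weight of the point. But the objective is comparative, and a reader cannot adjust an AE proportion from a separate exposure table.
- **CBR is not time on treatment.** It scores unassessed patients as non-responders, and treatment can also stop for toxicity or withdrawal of consent. This stands. A reader might infer that a 1.2- to 1.3-fold inflation follows from the plan's own 60% versus 40%. It does not: that figure also needs exponential durations, a persistent hazard and AEs of middling frequency.
- **The planning scenario did not occur.** Section 1.4 reports no numerical improvement in CBR or progression-free survival. This stands. A reader might go further and infer that venetoclax harm was understated, or that the AE tables hid a signal behind the 19 versus 9 deaths. The documents do not support that: they give no time on treatment, and the report is compatible with equal durations and no bias. Overall survival is analysed by Cox model from randomization, outside the AE window, and is untouched.
- **Noise is larger.** At a weekly hazard of 1% the artefact is 28.9% − 22.1% = 6.8 points. With 50 per arm, the 95% half-width is 1.96·√[(0.289·0.711 + 0.221·0.779)/50] = 17 points. This stands, but imprecision shows in an interval and this bias would not.
- **An exposure-adjusted rate can itself mislead.** Step 5 confirms it. Also, patients may stop venetoclax and continue fulvestrant (Sections 4.3.2.1 and 5.1.3.3), so combination-arm time includes time off venetoclax. Such a rate cannot carry the comparison.

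**Conclusion.** The point holds in a limited form. Section 6.5 has no AE summary that allows for unequal observation, although the length of full AE collection depends on a post-randomization outcome. If time on treatment differs between arms, crude proportions can mislead for AEs whose hazard persists; early-onset AEs are little affected.

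The size of 1.04 to 1.38 is a planning-stage illustration. It rests on the assumptions listed in the working and on the 60% versus 40% scenario. It is not an estimate of bias in the reported results. There the direction is unknown: none with equal durations, understated harm if the venetoclax arm stopped treatment sooner.

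**What to change.** In Section 6.5, for serious AEs, Grade 3 or higher AEs, AEs of special interest and AEs leading to discontinuation, add by arm:

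1. Incidence in a common early window, Weeks 0-8.
2. Cumulative incidence of first event, censored at the end of the AE window or data cut-off, with death as a competing event.

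State that the between-arm safety comparison is read from these two alongside the crude table. Exposure-adjusted first-event rates may be added as supportive only, with the constant-hazard caveat and with combination-arm time after stopping venetoclax reported separately.

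The cost is a paragraph of text and a few extra tables from data already collected; no visit, assessment or clinical rule changes. The small downside is that the early window misses late events, and that censoring at the end of treatment may be informative because patients stop for progression or toxicity. Showing both summaries lets each check the other.
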